7.2.7 Clinical laboratory assessments

The safety parameters that will be assessed at the clinical laboratory are listed in [Table 3](#). Routine clinical laboratory tests will be performed centrally. Samples for clinical laboratory parameters (biochemistry, hematology, coagulation) will be collected at screening (Visit 1), the dosing visit (Visit 2, prior to the start of the insulin-induced hypoglycemic procedure [within 30 minutes]) and at 30 and 300 minutes after dosing), and at the follow-up visit (Visit 3). The actual time of the assessment should not deviate from the nominal time by more than ± 10 minutes. Samples for glycated hemoglobin (HbA_{1c}) will be collected at screening only (Visit 1). Samples for urinalysis will be collected at screening (Visit 1), at the dosing visit (Visit 2, prior to the start of the insulin-induced hypoglycemic procedure [within 120 minutes]) and at the follow-up visit (Visit 3). The following parameters will be assessed:

- Clinical biochemistry: sodium, potassium, calcium, glucose, urea, creatinine, total bilirubin, AST, ALT, gamma-glutamyltransferase, alkaline phosphatase, total protein, C-reactive protein, HbA_{1c}, C-peptide.
- Hematology: hemoglobin, red blood cell count (erythrocytes), hematocrit, platelet count (thrombocytes), total white blood cell count (leukocytes).
- Coagulation: international normalized ratio, fibrinogen (at screening visit only).
- Urinalysis: pH, blood (leukocytes and erythrocytes), protein, glucose, ketones, nitrite.

Pregnancy tests will be performed at each visit for women of childbearing potential only. A serum pregnancy test will be performed at screening (Visit 1) and urine stick tests will be performed at the dosing visit (Visit 2, prior to the start of the insulin-induced hypoglycemic procedure) and the follow-up visit (Visit 3). Test sticks will be provided to the trial centers.

Alcohol breath tests and a urine drug screen will be performed at screening (Visit 1) and at the dosing visit (Visit 2, prior to the start of the insulin-induced hypoglycemic procedure). Equipment for the alcohol breath test and urine drug screen will be provided to the trial centers.

Re-assessment of laboratory parameters will be allowed only if handling issues, damaged samples, or hemolyzed samples have confounded the measurement results.

For further details of the clinical laboratory assessments, please refer to the laboratory manual.

7.2.8 *Pregnancy*

Female subjects must be instructed to notify the investigator immediately if they become pregnant or if they suspect to be pregnant during the trial. The sponsor has a responsibility to monitor the outcome of all pregnancies reported during the clinical trial.

Male subjects must be instructed to notify the investigator immediately if their partner becomes pregnant or suspects pregnancy. The sponsor has a responsibility to monitor the outcome of all pregnancies reported during the clinical trial. During an information meeting at the trial center, the subject's partner will be fully informed by a physician of her participation in capturing the outcome data, and will be asked to provide her written consent.

The investigator must report all information on pregnancies on the Initial Pregnancy form. The completed Initial Pregnancy form must be forwarded to the sponsor immediately (within 24 hours), according to the procedure stated in Section 7.2.1.2. Any (S)AEs in the mother, as well as other pregnancy complications (ectopic pregnancy) fulfilling the criteria of an (S)AE, must be reported on the (S)AE form.

The following must be collected in the Initial Pregnancy form:

- Medical history of the mother
- Family history
- Course of the pregnancy, including expected delivery date.

The investigator must follow the pregnancy until the pregnancy outcome and follow the newborn infant(s) until the age of 1 month. The investigator must collect information on the pregnancy and pregnancy complications as well as the pregnancy outcome including the health of the newborn infant(s) on the Pregnancy Outcome form. The completed Pregnancy Outcome form must be forwarded to the sponsor according to the procedure stated in Section 7.2.1.2. Any (S)AEs in the newborn must be reported on the (S)AE form.

The SAEs that must be reported include abnormal outcome, such as congenital anomalies, fetal death and termination of pregnancy (spontaneous or elective abortion), including any anomalies of the fetus observed at gross examination or during autopsy.

The following must be collected in the Pregnancy Outcome form:

- Course of the pregnancy
- Outcome of the pregnancy
- Condition of the newborn
- Any AEs in the newborn infant must be followed until the age of 1 month.

7.2.9 *Precautions*

Normal precautions taken for a human trial, including the provision of emergency equipment, will be taken during this trial. Qualified and well trained physicians and medical staff will instruct the subjects. During a subject's participation in the trial, the investigator should ensure that adequate medical care is provided to the subject for any AEs, including clinically significant laboratory values related to the trial. The investigator should inform the subject when medical care is needed for intercurrent illnesses of which the investigator becomes aware.

For further information on safety precautions for dasiglucagon and GlucaGen, please refer to the current version of the Investigator's Brochure (14) and the Summary of Product Characteristics for GlucaGen (13), respectively.

7.2.10 *Safety committee*

The internal Zealand Pharma Safety Committee is constituted to perform ongoing blinded safety surveillance of clinical trials with dasiglucagon, including this trial.

If safety signals are observed, either based on reported SAEs, periodic review of laboratory parameters, review of all AEs reported between the Safety Committee meetings, or on notification of significant findings, the Safety Committee will take appropriate measures to safeguard the subjects.

7.3 Demography, concomitant illness, medical history and concomitant medication

Demographics, body measurements, concomitant illness and medical history will be assessed only at screening (Visit 1). Concomitant medication will be assessed at screening (Visit 1), the dosing visit (Visit 2, prior to the start of the insulin-induced hypoglycemic procedure) and at the follow-up visit (Visit 3).

7.3.1 *Demography and body measurements*

Subject demographics and body measurements will include:

- Age
- Race, ethnicity
- Sex
- Height (meters or inch), without shoes
- Body weight (kg or lb), only wearing underwear and measured using standard scales
- Body mass index (kg/m²) calculated based on height and body weight (body weight/height²).

7.3.2 *Concomitant illness and medical history*

A concomitant illness is any illness that is present at the start of the trial (i.e. at the screening visit). Concomitant illnesses present at the start of the trial will be recorded in the eCRF at screening.

Medical history is an account of medical events that the subject has experienced in the past, including prior medications. Relevant medical conditions/illnesses in the past obtained by asking the subject or by inspecting his/her medical records will be recorded in the eCRF at screening. History of alcohol or drug abuse will also be recorded.

The information collected for concomitant illness and medical history should include diagnosis, date of onset, date of resolution or continuation.

Any change to a concomitant illness should be recorded during the trial, including end date, if applicable. A clinically significant worsening of a concomitant illness must be reported according to Section [7.2.1](#).

All previous and concomitant diseases will be coded with Medical Dictionary for Regulatory Activities (MedDRA), the version of which will be provided in the clinical trial report.

7.3.3 *Diabetes diagnosis and current treatment*

The date of diagnosis of diabetes will be recorded as will the current diabetes treatment (start date, product name(s), dose(s)).

7.3.4 *Concomitant medication*

A concomitant medication is any medication, other than the trial products and current diabetes treatment (including insulin glulisine [Apidra[®]] for diabetes therapy wash-out), which is taken during the trial, including screening and follow-up periods.

Details of any concomitant medication must be recorded at trial entry (i.e. at screening). Any changes in concomitant medication must be recorded at each visit as they occur. The information collected for each concomitant medication includes (at a minimum) trade name or generic name, indication, start date and stop date or continuation. A change in medication due to an AE must be recorded and reported according to Section 7.2.1. If the change in medication influences the subject's eligibility to continue in the trial, the sponsor and trial monitor must be informed.

7.4 Other assessments

7.4.1 Immunogenicity

Antibodies against dasiglucagon/GlucaGen will be measured at the dosing visit (Visit 2) and at follow-up (Visit 3). At the dosing visit (Visit 2), samples will be collected prior to the start of the insulin-induced hypoglycemic procedure.

The clinical ADA assays, specific for dasiglucagon and GlucaGen, respectively, have been validated in accordance with existing guidelines and recommendations (17-21).

Confirmed positive anti-dasiglucagon antibody samples (treatment-induced or treatment-boosted) from anti-dasiglucagon antibody-positive subjects will be evaluated for binding titer neutralizing potential and titer as well as cross-reactivity towards endogenous glucagon.

No further serum sampling will be needed as the ADA samples can be used for neutralizing antibody analysis.

The in vitro neutralizing effect of the antibodies will be measured using an assay based on glucagon receptor transfected human embryonic kidney cells (20,22). The calculated sensitivity in previous studies was about 51.8 ng/mL. The assay was also validated for recombinant glucagon with similar results (21,23). In case of a positive result in the neutralizing antibody assay, a titer estimation will be performed. The cell-based neutralizing antibody analyses will be performed by a special laboratory, BioAgilytix, Durham, NC, USA.

Residual and additional antibody serum samples may be stored until approval of market authorization by the health authorities. Further characterization of the antibody response may be requested by the health authorities.

7.4.2 *Plasma glucose measurements for safety*

During insulin-induced hypoglycemia, plasma glucose levels will be monitored closely at site. After the start of insulin infusion, plasma glucose should be checked every 10 minutes while plasma glucose is above 110 mg/dL, and every 5 minutes once plasma glucose is at or below 110 mg/dL and until after dosing when the subject's plasma glucose is ≥ 70 mg/dL (3.9 mmol/L). Hereafter, plasma glucose should be checked every 30 minutes until 300 minutes (5 hours) after dosing. Plasma glucose concentrations will be measured using a US FDA-approved glucose analyzer (e.g., YSI 2300, Yellow Springs Instruments, Yellow Springs, OH).

At the discretion of the investigator, additional plasma glucose measurements can be taken at any time during the trial, for example when there is a suspicion (e.g. symptoms) of a hypoglycemic episode.

Plasma glucose measurements for safety should only be recorded in the eCRF if they are related to an AE (e.g. a hypoglycemic episode).

In case of persistent post-treatment hypoglycemia, subjects will receive rescue treatment with an IV glucose infusion (see Section 8.2.3.1 for details). Blood samples for PD and PK assessments should still be taken at the specified timepoints.

7.4.3 *Plasma insulin measurements*

Samples for insulin assessment will be collected at the dosing visit (Visit 2, pre-dose and at 30 and 60 minutes after dosing). The actual time of blood sampling for evaluation of plasma insulin should not deviate from the nominal time by more than ± 1 minute. Pre-dose is defined as within 2 minutes prior to dosing.

8 TRIAL CONDUCT

8.1 Schedule of procedures

The schedule of procedures is provided in [Table 3](#). Informed consent will be obtained prior to any trial-related procedures; see Section [10.8](#).

8.2 Procedures by visit

8.2.1 *Visit 1 (screening, Day -30 to Day -3)*

Visit 1 will take place between 3 and 30 days before Visit 2, Day -1 to Day 1 (dosing day).

Informed consent can be obtained prior to or at Visit 1, however it must in any case be obtained prior to any trial related procedures. During the screening visit, the following assessments will take place:

- Informed consent (obtain or check)
- Check of subject eligibility (inclusion/exclusion criteria)
- Demography
- Body measurements
- Medical history, diabetes diagnosis, current diabetes treatment
- Concomitant illnesses
- Concomitant medications
- History of alcohol/drug abuse
- Physical examination
- Vital signs
- 12-lead ECG
- AEs
- Biochemistry, hematology, coagulation, HbA_{1c}
- Serum pregnancy test (women of childbearing potential only)
- Urinalysis
- Urine drug screen
- Alcohol breath test

Table 3 Schedule of procedures

Visit number	V1	V2	V3
Trial day	-3	-1 and 1	28
Visit type	Screening	Dosing	Follow-up
Window	-30 to -3		+5 days
Subject related information/assessments			
Informed consent	x		
Inclusion/exclusion criteria	x	x ^{1,2}	
Demography	x		
Body measurements	x		
Medical history, diabetes diagnosis, and current diabetes treatment	x		
Concomitant illnesses	x		
Concomitant medications	x	x ¹	x
History of alcohol/drug abuse	x		
Randomization		x ¹	
Withdrawal criteria		x ¹	
Dosing day exclusion criteria		x ¹	
Insulin-induced hypoglycemia		x	
Safety assessments			
Physical examination	x		x
Vital signs	x	x ³	x
12-lead ECG	x	x ⁴	x
Local tolerability		x ⁵	x
Adverse events	x	x	x
Laboratory			
Biochemistry, hematology, coagulation, HbA _{1c} (HbA _{1c} at Visit 1 only)	x	x ⁶	x
Pregnancy test (women of childbearing potential only)	x ⁷	x ^{1,8}	x ⁸
Urinalysis	x	x ¹	x
Urine drug screen	x	x ¹	
Alcohol breath test	x	x ¹	
PK/Clinical efficacy			
Plasma dasiglucagon/GlucaGen		x ⁹	
Plasma glucose		x ¹⁰	
Other assessments			
Antibodies against dasiglucagon/GlucaGen		x ¹	x ¹¹
Plasma insulin		x ¹²	
Trial material			
Administration of trial product (during hypoglycemic clamp procedure)		x	

¹Prior to the start of the insulin-induced hypoglycemic procedure.

²Only check of dosing day exclusion criteria and changes between screening visit and Visit 2.

³Prior to the start of the insulin-induced hypoglycemic procedure (within 30 minutes), and at 30, 90 and 300 minutes after dosing. The actual time of the assessment should not deviate from the nominal time by more than ±10 minutes.

⁴Prior to the start of the insulin-induced hypoglycemic procedure (within 30 minutes), and at 20, 35, 45, 60 and 300 minutes after dosing. The actual time of the assessment should not deviate from the nominal time by more than ± 5 minutes.

⁵Local tolerability assessed at 30, 120, and 300 minutes after dosing. The actual time of the assessment should not deviate from the nominal time by more than ± 10 minutes.

⁶Prior to the start of the insulin-induced hypoglycemic procedure (within 30 minutes), and at 30 and 300 minutes after dosing. The actual time of the assessment should not deviate from the nominal time by more than ± 10 minutes.

⁷Serum pregnancy test.

⁸Urine stick pregnancy test.

⁹Pre-dose, and at 15, 30, 35, 40, 50, 60, 90, and 120 minutes after dosing. The actual time of blood sampling should not deviate from the nominal time by more than ± 1 minute. Pre-dose is defined as within 2 minutes prior to dosing.

¹⁰Pre-dose, and at 4, 6, 8, 10, 12, 15, 17, 20, 25, 30, 40, 50, 60, 75, 90 minutes after dosing. The actual time of blood sampling should not deviate from the nominal time by more than ± 30 seconds until the 20 minute collection time point and by more than ± 1 minute for the subsequent collection time points. Pre-dose is defined as within 2 minutes prior to dosing.

¹¹Any subject that tests positive for ADA will be monitored until the ADA levels return to baseline levels.

¹²Pre-dose, and at 30 and 60 minutes after dosing. The actual time of blood sampling should not deviate from the nominal time by more than ± 1 minute. Pre-dose is defined as within 2 minutes prior to dosing.

ADA = anti-drug antibodies; ECG = electrocardiogram; HbA_{1c} = glycated hemoglobin.

Eligible or potentially eligible subjects (laboratory results pending) will be provided with an Identification card (ID card), stating that the subject is participating in the trial and whom to contact (site address, investigator name and telephone number). The subjects should be instructed to return the ID card to the investigator at the last visit or to destroy the card after the last visit.

8.2.2 Instructions to subjects prior to the dosing visit (Visit 2)

At the screening visit, the investigator will inform the subject about the changes to his/her insulin therapy leading up to the start of the insulin-induced hypoglycemic procedure. The subject may be provided with insulin NPH in the wash-out period to cover the need of basal insulin, if deemed necessary by the investigator. The subject's current insulin therapy will be washed out as defined in Section 5.5.: 48 hours prior to dosing and during the dosing visit, treatment with insulin Degludec and insulin Glargine U300 are not allowed; 24 hours prior to dosing and during the dosing visit, treatment with other long-acting insulins (e.g., insulin Glargine U100 or insulin Detemir) is not allowed; 16 hours prior dosing and during the dosing visit treatment with insulin NPH is not allowed; 6 hours prior to dosing and during the dosing visit, treatment with any short acting (bolus) insulin, except insulin glulisine (Apidra[®]), is not allowed. The basal rate of insulin pumps (continuous SC insulin infusion) will be discontinued on the morning of the dosing day (if using insulin glulisine [Apidra[®]]) OR at least 6 hours prior to dosing (if using other insulins).

On the day prior to dosing (Day -1), the subjects will need to attend the clinical center and will be required to stay onsite overnight. On the morning of the dosing day (Day 1), patients are required to be in a fasting condition, defined as having consumed only water since 22:00 hours the night before. However, the subjects are allowed to consume small

amounts (up to 20 g) of carbohydrates to prevent hypoglycemia. The subjects must also not consume any alcohol within 24 hours prior to dosing (refer to Section [5.5](#) for all dosing day exclusion criteria).

8.2.3 Visit 2 (dosing visit)

Visit 2 will take place on Day -1 to Day 1.

The subjects will attend the clinical center the day prior to dosing (Day -1) and subject eligibility is rechecked (check of changes between the screening visit and Visit 2) and those subjects eligible to participate should stay onsite overnight. To target a glucose level around 90-110 mg/dL (5.0-6.1 mmol/L) the following morning, subjects may be administered insulin glulisine (Apidra®) at the investigator's discretion either by IV infusion, SC bolus or continuous SC insulin infusion. Dosing will take place the following morning (Day 1).

On Day 1 and prior to the start of the insulin-induced hypoglycemic procedure, those subjects eligible to participate will be randomized to treatment with dasiglucagon, placebo, or GlucaGen.

The following assessments will also take place:

- Document all changes in concomitant medication (prior to the start of the insulin-induced hypoglycemic procedure)
- Check of withdrawal criteria (prior to the start of the insulin-induced hypoglycemic procedure)
- Check of dosing day exclusion criteria (prior to the start of the insulin-induced hypoglycemic procedure)
- Vital signs (prior to the start [within 30 minutes] of the insulin-induced hypoglycemic procedure, and at 30, 90 and 300 minutes after dosing). 12-lead ECG (prior to the start [within 30 minutes] of the insulin-induced hypoglycemic procedure, and at 20, 35, 45, 60, and 300 minutes after dosing)
- Local tolerability (at 30, 120, and 300 minutes after dosing)
- AEs
- Biochemistry, hematology, coagulation (prior to the start of the insulin-induced hypoglycemic procedure [within 30 minutes], and at 30 and 300 minutes after dosing)
- Urine stick pregnancy test (women of childbearing potential only; prior to the start of the insulin-induced hypoglycemic procedure)
- Urinalysis (prior to the start of the insulin-induced hypoglycemic procedure [within 120 minutes])
- Urine drug screen (prior to the start of the insulin-induced hypoglycemic procedure)
- Alcohol breath test (prior to the start of the insulin-induced hypoglycemic procedure)

- Dasiglucagon/GlucaGen plasma concentrations:
 - Pre-dose, 15, 30, 35, 40, 50, 60, 90, and 120 minutes after dosing. The actual time of blood sampling for exposure should not deviate from the nominal time by more than ± 1 minute. Pre-dose is defined as within 2 minutes prior to dosing.
- Plasma glucose concentrations:
 - Pre-dose, 4, 6, 8, 10, 12, 15, 17, 20, 25, 30, 40, 50, 60, 75, and 90 minutes after dosing. The actual time for blood sampling for plasma glucose should not deviate from the nominal time by more than ± 30 seconds until the 20 minute collection time point and by more than ± 1 minute for the subsequent collection time points. Pre-dose is defined as within 2 minutes prior to dosing.
- Antibodies against dasiglucagon/GlucaGen (prior to the start of the insulin-induced hypoglycemic procedure).
- Plasma insulin concentrations:
 - Pre-dose, 30 and 60 minutes after dosing. The actual time of blood sampling for plasma insulin should not deviate from the nominal time by more than ± 1 minute. Pre-dose is defined as within 2 minutes prior to dosing.

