9.5.5 Exposure (PK) endpoints

- Plasma dasiglucagon and GlucaGen concentrations from time zero to 90 minutes: $AUC_{0-90min}$, C_{max} , and t_{max} .

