9.5.5.1 Analysis of exposure (PK) endpoints

AUC will be derived as the area under the individual plasma dasiglucagon/GlucaGen concentration profile for PK from 0 to 90 minutes or last valid measurement if this measurement is assessed sufficiently close to 90 minutes (decision to be taken at the masked data review meeting). The standard trapezoidal method will be used, based on actual rather than nominal timepoints.

C_{max} will be determined as the maximum of all valid plasma dasiglucagon/GlucaGen concentrations.

T_{max} will be determined as the timepoint where the maximum of all valid plasma dasiglucagon/GlucaGen concentration measurements for each measurement series is observed.

The log-transformed PK endpoints AUC and C_{max} will be analyzed in the same way as the AUC endpoints.

As t_{max} is a highly discrete endpoint, Wilcoxon's rank sum test for unpaired observations will be used to assess differences between the two treatment groups.

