2.1.3.1 Pharmacokinetics and pharmacodynamics of dasiglucagon

The results of the phase 1 and 2 clinical trials confirmed dose-proportionality for dasiglucagon PK, which is characterized by a fast absorption with a peak plasma concentration obtained after 35 minutes. Thereafter, the plasma concentration rapidly declines with an average half-life of 28 minutes. The median time to the maximum plasma concentration (t_{max}) was 35 minutes for dasiglucagon compared with 20 minutes for GlucaGen.

At all dose levels in the phase 2 trial, all subjects achieved a plasma glucose level of at least 70 mg/dL (3.9 mmol/L) as well as an increase in plasma glucose by at least 20 mg/dL (1.1 mmol/L) within 30 minutes after dosing. The PD responses to 0.6 mg of dasiglucagon and 1 mg of GlucaGen were comparable.

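### PK sampling jumps from 15 to 30 minutes, so GlucaGen's expected tmax of 20 minutes cannot be recorded; one extra aliquot from a blood draw already scheduled would repair it

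*Protocol*

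**What the plan says.** - **PK schedule.** Protocol Section 8.2.3 samples "Pre-dose, 15, 30, 35, 40, 50, 60, 90, and 120 minutes after dosing". It adds that "The actual time of blood sampling for exposure should not deviate from the nominal time by more than ± 1 minute". Section 7.1.2 and Tables 3 and 4 give the same times, and so does every version of the schedule in the file.
- **Expected peaks.** Section 2.1.3.1 reports from earlier trials that median tmax "was 35 minutes for dasiglucagon compared with 20 minutes for GlucaGen". It also says that the dasiglucagon concentration "rapidly declines with an average half-life of 28 minutes". It gives no half-life for GlucaGen.
- **Derivation.** Under Section 9.5.5.1, Cmax "will be determined as the maximum of all valid plasma dasiglucagon/GlucaGen concentrations", and tmax is the time of that observation. No model or interpolation is used.
- **Comparison.** For tmax, "Wilcoxon's rank sum test for unpaired observations will be used to assess differences between the two treatment groups". Log Cmax and log AUC are compared by ANCOVA as ratios of geometric means.
- **Glucose schedule.** At the same visit, blood for plasma glucose is drawn "Pre-dose, 4, 6, 8, 10, 12, 15, 17, 20, 25, 30, 40, 50, 60, 75, and 90 minutes after dosing".

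Section 2.1.3.1 appears in the versions shown in full. The first part of the version that opens the file is not shown.

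**The concern.** The sampling times suit one of the two drugs. Around the dasiglucagon peak they are 5 minutes apart; around the GlucaGen peak there is nothing between 15 and 30 minutes, and the protocol gives no reason. Since tmax can only be a time at which blood was taken for PK, the comparator's tmax is pushed to one edge of the gap or the other.

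AUC0-90, Cmax and tmax are named secondary endpoints (Section 3.5). The difference in tmax between a new rescue product and the established one is likely to be quoted. A sample that was never taken cannot be recovered in the analysis, so this has to be settled in the schedule.

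**Working it through.** **1. What follows without any model.** With the ±1-minute window, samples near the GlucaGen peak are taken at 14–16 or 29–31 minutes. A recorded tmax near 20 is impossible.

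**2. Single profiles.** I assumed one compartment with first-order absorption:

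C(t) ∝ exp(−ke·t) − exp(−ka·t), with ke = ln 2 / half-life and tmax = ln(ka/ke)/(ka − ke).

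The GlucaGen tmax of 20 minutes comes from Section 2.1.3.1. Its half-life is not documented and was varied over 5–45 minutes.

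Example with half-life 20 minutes: ke = 0.0347 and ka = 0.0693 give tmax = ln 2 / 0.0347 = 20. Because ka = 2ke, C(t) ∝ x − x² with x = 2^(−t/20).
- t = 20: 0.5 − 0.25 = 0.2500
- t = 15: 0.5946 − 0.3536 = 0.2410, which is 96.4% of the peak
- t = 30: 0.3536 − 0.1250 = 0.2286, which is 91.4% of the peak

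The subject is recorded at 15 minutes, with Cmax 3.6% low. Across the assumed half-lives:

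| True GlucaGen tmax | Recorded tmax | Observed Cmax / true Cmax |
|---|---|---|
| 20 min | 15 min | 0.963–0.976 |
| 22 min | 30 min | 0.948–0.976 |
| 25 min | 30 min | 0.983–0.993 |

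A dasiglucagon profile with tmax 35 and half-life 28 minutes is recorded at 35 minutes with its full Cmax.

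**3. A group of subjects.** The recorded time switches from 15 to 30 where C(15) = C(30). Solved numerically, this is at a true tmax of about 21.2–21.6 minutes for half-lives of 5–40 minutes. If tmax is lognormal with median 20, more than half the subjects lie below that point, so the recorded median is 15 whatever the spread. Taking 21.6, ln(21.6/20) = 0.077, and the share recorded at 15 is:
- log-SD 0.2: Φ(0.077/0.2) = 65%
- log-SD 0.3: Φ(0.077/0.3) = 60%
- log-SD 0.4: Φ(0.077/0.4) = 58%

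Simulation with half-life 10–28 minutes agrees: 57–66% at 15, 31–35% at 30, the remainder later. The recorded median is 15 for GlucaGen and 35 for dasiglucagon. The difference in medians reads 35 − 15 = 20 minutes, against 35 − 20 = 15 from the stated values.

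**4. Cmax ratio.** In the same simulations, mean observed/true Cmax is 0.974–0.982 for GlucaGen and 0.993–0.997 for dasiglucagon. The dasiglucagon/GlucaGen ratio is inflated by 1.1–2.0%.

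**5. AUC0-90.** For a GlucaGen profile peaking at 20 minutes, the trapezoid on the planned times gives 95.6–95.9% of the true area. Adding 20 and 25 minutes gives 96.0–96.8%, a gain of 1 point or less. Most of the shortfall arises before 15 minutes. Dasiglucagon is at 98.0% on the planned times, so the ratio is off by about 2%.

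**6. With the extra samples.** Adding 20 minutes alone restores the simulated GlucaGen median to 20 in every scenario. Adding 25 minutes as well cuts the share recorded at 30 from 14–20% to 5–10%. The bias in the Cmax ratio falls to 0.1–1.2%.

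**The case against.** Most of the case against stands and limits the point.

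- **No decision rests on it.** The secondary objective concerns glycemic response, not PK. PK is outside the hierarchy of Section 9.5.1, and the synopsis calls dasiglucagon versus GlucaGen descriptive. Section 9.5.5.1 does plan a Wilcoxon test and an ANCOVA, but attaches no margin or claim to them. The glucose endpoints use their own dense schedule.
- **The ordering of the drugs is kept.** A reader might infer that the sampling times create the tmax contrast. They do not: 15 and 30 both rank below 35. In simulation with 78 against 39 subjects (assumed 30% between-subject SD and 5% assay noise), the Wilcoxon test was significant in every run, with or without the extra samples. The median pairwise shift was about 16 minutes on the planned times and 13 with 20 and 25 added. The times distort the size of the difference by a few minutes.
- **The Cmax error is small beside the random error.** With an assumed 30% variability, the 95% interval for the ratio is about ±1.96 × 0.3 × √(1/78 + 1/39) = ±0.115 on the log scale, or roughly ±12%. The bias is 1–2%.
- **The inputs are partly unknown.** GlucaGen's half-life and the spread of tmax are assumed. The 20-minute median is itself an observed value from earlier trials whose sampling times are not given.

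What remains is step 1, which needs no assumption: the expected comparator peak lies where no PK sample is taken, although blood is drawn at that minute for glucose.

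**Conclusion.** The point holds as a minor, cheap improvement. It is certain that GlucaGen tmax cannot be recorded near the protocol's own expected value. Under smooth one-compartment kinetics with a true median of 20 minutes, the recorded median reads 15 and the difference in medians is overstated by about 5 minutes, one third of the stated 15. Cmax is understated by about 2–5% for a GlucaGen profile peaking at 20–22 minutes and by 1–2% in the average ratio; a sharper peak than this model allows would make that larger. The errors do not all favour one drug: the tmax error makes GlucaGen look faster, while the Cmax error raises the ratio in favour of dasiglucagon.

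Two wider conclusions might be drawn and are not supported. One is that the gap makes AUC0-90 materially wrong; filling it gains 1 point or less. The other is that AUC should run to 120 minutes because a sample is taken then. The endpoint covers "Plasma dasiglucagon and GlucaGen concentrations from time zero to 90 minutes", is defined that way throughout, and applies alike to both drugs, so extending it would be a preference and not a correction.

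**What to change.** Add a PK aliquot at the 20-minute blood draw already scheduled for glucose, and preferably one at 25 minutes, keeping all existing times. Amend Sections 7.1.2, 8.2.3 and 8.2.3.1, Tables 3 and 4, and the laboratory manual to match. The analysis in Section 9.5.5.1 needs no change. The cost is one or two extra assays and a few mL of blood per subject, on top of the roughly 180 mL already planned (Section 7), with no new visit or venipuncture.

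If the schedule stays as it is, the report should state that GlucaGen tmax could only be observed at about 15 or 30 minutes in the region of its expected peak, and should present the tmax difference with that limitation.
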